At the moment of trial design (2018), no data were available on an RCT investigating changes in muscle size after PRT in a population of children with SCP. Therefore, effect sizes (d) of systematic reviews and meta-analyses reporting muscle strength outcomes after PRT were used. Reported effect sizes were moderate ($d=0.53$) (Ryan et al., 2017) and large ($d=1.050$ and $d=1.105$) (Park & Kim, 2014). Based on a large effect size of $d=0.8$ with the probability of making a type I error set equal to or less than 1% ($p\leq 0.01$) and a power of 80%, an independent samples t-test with common standard deviation required 39 independent observations per group to compare the evolution over time between the intervention and control groups. To account for the possibility of clustered legs in bilaterally affected participants a design effect (Killip et al., 2004) was calculated resulting in an estimated sample size of clustered observations per group with following formulas:

$$\text{Design effect} = 1 + \rho * (m-1),$$

where ρ is the intraclass correlation and m the cluster size, and,

$$\text{Estimated sample size of clustered legs} = \text{estimated sample size of independent observations} * \text{design effect} = m * \text{number of participants}$$

With a cluster size of $m=2$ (2 legs per bilaterally affected participant) and an intraclass correlation coefficient of $\rho=0.1$, based on literature of general health parameters (Adams et al., 2004), the estimated design effect was 1.1, resulting in 43 clustered legs, or 22 bilaterally affected participants per group. A group including both uni- and bilaterally affected children would require a sample size between 39 and 43.

Intervention

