Endurance functional strength will be assessed with 30-s repetition maximum tests including bi- and unilateral heel raise, sit-to-stand, and lateral step-up, as previously described (van Tittelboom et al., 2021). Participants completed as many repetitions as possible in 30 seconds. Each test will be 3 times and the average taken as final score. Explosive strength will be evaluated with a standing long jump, with both feet together, which will also be repeated 3 times and the scores averaged. The use of orthoses will not be allowed, as the PRT program will also be performed without orthoses.

5. Gross motor function and walking capacity

Gross motor function will be evaluated with the Gross Motor Function Measure-Item Set (Brunton & Bartlett, 2011) and the Gross Motor Ability Estimator 2 used to estimate the final score. The 1-minute walk test, performed on an indoor 20-m track, will be used to assess walking capacity (Chrysagis et al., 2014; McDowell et al., 2009). The participant will be instructed to walk as fast as possible without running and the distance covered in 1 minute will be recorded. Both assessments will be performed without orthoses, but a key-walker is allowed for the 1-minute walk test for children classified as GMFCS-level III.

6. Statistics

Descriptive statistics for all groups will be summarized using appropriate summary indices. The comparison between TD children and children with CP will be performed with a Student's *t*-test (after confirming equality of variances) or the Mann-Whitney *U*-test. Associations between muscle morphology measures, muscle strength and participant characteristics will be evaluated with univariate linear regressions followed by a multivariate linear regression using a backward approach. The linear regressions in the TD cohort based on an anthropometric variable will be used to define the deficits in muscle strength and muscle morphology in CP children.

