To define the effects of the PRT intervention linear mixed models will be applied to evaluate the difference in evolution over time between the control and intervention group (time*group interaction effect) and between PRE and POST within each group (time effect). The random effects in these models can correct for the correlation between repeated observations within the same subject. Moreover, in the case of missing values that are completely at random, i.e. not related to any observed or unobserved outcomes, or at random, i.e. related to observed outcomes, linear mixed models provide valid inferences for missing observations. A covariance structure for repeated measurements to model longitudinal dependencies within the participant will be applied with a random intercept for participant (legs are nested within participants). The models will be adjusted for age and GMFCS level as covariates as these were used to allocate the children to the control or intervention group. Age was entered as a categorical variable (<8 years and >8 years). A full-factorial time*group mean model adjusted for age and GMFCS level, with a compound symmetry covariance matrix, unless an unstructured covariance matrix results in a better fit (Akaike information criterion decrease of >2). Adjustment for age (categorical variable: <8 years and >8 years) and GMFCS level will be included as these were used to allocate the children to the control or intervention group.

The α -level will be adjusted to $p \leq 0.01$ since multiple parameters are evaluated for most research questions, with a maximum of 5 parameters (functional strength). All analyses will be performed with SPSS (Version 28, SPSS Inc., Chicago, Illinois).

Finally, the data of the total intervention group (intervention + waitlist control group with delayed intervention) will be used to define the association between baseline properties and the changes in the outcome parameters after PRT with uni- or multivariate regression (mixed) models.

References

<https://doi.org/10.1016/j.jclinepi.2003.12.013>

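### The association models are chosen by univariate regressions and backward elimination with no correction for that selection, so weak slopes that survive will be overestimated

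*Combined protocol and SAP*

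**What the plan says.** Section 6 (Statistics), first paragraph, states the aim: "Associations between muscle morphology measures, muscle strength and participant characteristics will be evaluated". The method is "univariate linear regressions followed by a multivariate linear regression using a backward approach".

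The section does not say which variables are candidates, which variable is the outcome, or whether a univariate result decides entry to the larger model. It also gives no removal threshold, no number of children, and no shrinkage, validation or optimism correction.

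The only multiplicity provision is the 0.01 level later in the same section. It is justified "since multiple parameters are evaluated for most research questions, with a maximum of 5 parameters (functional strength". That reason concerns the number of outcome parameters per question, not a search over predictors. Whether 0.01 also governs these regressions, or the removal step, is not explicit.

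The Sample size section sizes the trial for the between-group comparison, using "an independent samples t-test with common standard deviation". It does not size these regressions.

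**The concern.** In backward elimination the same data choose the model and estimate its slopes. A weak predictor stays only in samples where its estimate happens to be large, so the reported slope is too large on average. A variable that has survived elimination also no longer has its nominal chance of a small p-value.

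At stake is the account of which muscle properties and child characteristics go with strength. Weak associations could be reported as moderate ones, and some reported predictors could be chance findings.

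**Working it through.** **1. The plan's own sample size, which bounds the number of children.** Inputs from the Sample size section: d=0.8, alpha 0.01, power 80%, ICC 0.1, cluster size 2. Sidedness is not stated; two-sided is assumed.

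- Normal approximation: 2(2.576+0.842)²/0.8² = 36.5, so 37 per group. The exact noncentral t gives 39 (power 0.810). This reproduces the plan's 39; a one-sided test would give 33.
- Design effect: 1+0.1×(2−1) = 1.1. Then 39×1.1 = 42.9, so 43 legs, and 43/2 = 21.5, so 22 bilaterally affected children. Reproduced.
- Both groups together: 2×22 = 44 if all are bilaterally affected, up to 2×39 = 78 with one leg per child. Using 44-78 for the association analysis is an assumption.

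**2. Candidates (assumed).** Section 1 (Participant characteristics) records age, body mass, height, range of motion, spasticity, manual strength and selective motor control. The eligibility criteria add GMFCS level, and Section 3 adds muscle volume, length and echo-intensity. Total: 7+1+3 = 11.

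**3. Why retained slopes are inflated: a hand check.** Take uncorrelated standardised predictors, residual SD 1 and removal at p>0.10. The standard error is about s = 1/√n, and a slope b stays if b̂/s exceeds the critical value c. With δ = b/s, its mean given retention is about b + s·φ(c−δ)/Φ(δ−c).

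- n=44, b=0.20: s=0.151, δ=1.33, c=1.69. Mean = 0.20+0.151×0.374/0.360 = 0.36.
- n=78, b=0.20: s=0.113, δ=1.77, c=1.67. Mean = 0.20+0.113×0.397/0.540 = 0.28.
- n=78, b=0.50: δ=4.42. Mean = 0.50+0.113×0.009/0.997 = 0.50.

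Simulated backward elimination with 5-10 uncorrelated candidates and no screen gives 0.36-0.37, 0.29 and 0.50-0.51. Inflation is large for weak slopes and close to nil for strong ones.

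**4. Slope inflation with 11 candidates.** Simulation assumptions: pairwise correlation 0.3 (0.85 among age, mass and height), one true slope of 0.25 SD, removal at p>0.10, 1500 runs per setting. Overestimation when the predictor is retained:

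| n | no univariate screen | screen at p≤0.10 |
|---|---|---|
| 44 | 60% | 52% |
| 60 | 43% | 34% |
| 78 | 33% | 25% |

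A separate set of runs gave 30-61% without a screen and 25-52% with one. At n=60 without a screen, the true predictor is kept in about 55% of runs. A slope of 0.50 SD is inflated by about 4% at n=60.

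**5. False-positive rate per predictor at 0.01.** Grid: n=44 and 78; 5, 10 or 15 candidates; correlation 0, 0.5 or 0.8; removal at 0.10, 0.05 or 0.01; 3000 runs per cell under the global null.

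| Procedure | Rate |
|---|---|
| Backward, no screen | 0.010-0.049 |
| Backward after a univariate screen | 0.003-0.013 |
| Full model, no selection | 0.008-0.012 |

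With a screen and a true predictor correlated 0.5 with the null ones (screen and removal both at 0.05), the rate is 0.009-0.018.

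**6. R-squared at n=60, same correlations as step 4, no screen (apparent / in new data).**

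| Model | No true association | One slope of 0.25 |
|---|---|---|
| Backward from 11 | 0.095 / −0.13 | 0.148 / −0.09 |
| Full model, 11 predictors | 0.188 / −0.26 | 0.233 / −0.18 |
| Fixed model, 5 predictors | 0.086 / −0.11 | 0.137 / −0.05 |

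The null expectation for an unselected model is k/(n−1): 5/59 = 0.085 and 11/59 = 0.186, which match. The fixed five-predictor model is nearly as optimistic as the backward model.

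**The case against.** The strongest reply is that this is a secondary, descriptive analysis whose details are open, and that the size of the problem comes from assumptions. Much of that stands. The plan names no candidate count, removal level or analysis size. Torque is already normalised to body weight, and volume and length to fibula length, so age, mass and height might not all be entered. The plan also does not say how p-values or R-squared from the selected model will be interpreted.

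Four stronger readings are tempting but not supported:

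- A reader might infer that the false-positive rate doubles. That is one point in a range from no excess to 4.9 times nominal without a screen. Univariate regressions placed before the larger model can naturally be read as a screen, and the null rate is then near or below 0.01.
- A reader might blame backward elimination for the optimistic R-squared. Unselected models of similar or larger size do no better at n=60; the cause is mainly the small cohort.
- A reader might extend the point to the final analysis in Section 6, which aims "to define the association between baseline properties and the changes in the outcome parameters after PRT with uni- or multivariate regression (mixed) models". That text mentions no backward selection.
- A reader might doubt the trial's main result. The time-by-group model has fixed covariates (age category and GMFCS level) and involves no such selection.

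The reply does not remove the slope bias. It follows from the stated procedure and is present with or without a screen.

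**Conclusion.** The concern holds in limited form. Followed as written, the plan overestimates weak associations that survive selection, and nothing in it corrects for this. The figures of about 25-60% for a slope of 0.25 SD and about 4% for 0.50 SD assume 11 candidates and removal at p>0.10, with 44-78 children for the first and 60 for the second. An excess of false positives is possible but depends on whether the univariate step screens, which the plan should state. The optimism in R-squared is real but not specific to elimination. The change is worth making because it is cheap, but it concerns a secondary analysis only.

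**What to change.** In Section 6, first paragraph, replace the backward approach with one pre-specified model per strength outcome. This takes strength as the outcome, which the plan should confirm. List a small set of predictors chosen on subject grounds, state the number of children and the significance level, and report the model in full without elimination. Keep the univariate results as description. Report a bootstrap optimism-corrected R-squared, which is needed even without selection (step 6).

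If backward selection is kept, state the candidates, the role of the univariate step and the removal level. Repeat the whole selection, univariate step included, inside each bootstrap sample, and label the result exploratory.

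The cost is a few sentences of SAP text and a short bootstrap, with no new data. The downside is less tidy models and a lower reported R-squared. A fixed model restores the rate per predictor, not per model: with five independent predictors tested at 0.01, the chance of at least one false positive is still 1−0.99⁵ = 0.049.

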Age, body mass and height will be recorded for the participants at each assessment. Usual care and treatment history will be recorded at the PRE-assessment using standardized in-house questionnaires. A routine clinical examination regarding the investigated muscle groups will be performed, including passive joint range of motion, spasticity, manual muscle strength and selective motor control (SMC), based on standard clinical scales (Bohannon & Smith, 1987; Boyd, 1999; Gage et al., 2009; Matthews, 1977). These clinical examination parameters will be used to define the most affected leg for bilaterally affected children. If both sides are equally affected, the right leg will be used. Lower limb SMC will be assessed with the selective control assessment of the lower extremity total limb score (Fowler et al., 2009). Assessments will be performed in the same order, starting with clinical examination and muscle morphology, followed by isometric and functional strength and lastly gross motor function and walking capacity.

2. Isometric strength assessments

Knee extensor, knee flexor and plantar flexion maximum voluntary isometric contractions were collected with a fixed dynamometer in a previously described, custom-designed chair (Goudriaan et al., 2018). The dynamometer is positioned at 75% of the lower leg and foot length, and the level arm distance is measured between this position and the joint axis. After a test trial, we aim to collect 3 well executed maximum voluntary isometric contractions with a duration of 3 to 5 seconds. Standardized verbal encouragement and visual feedback will be provided throughout the isometric contraction. The protocol includes periods of rests of at least 10 seconds between repeated

assessments and of at least 2 minutes between different muscle groups. Peak force is extracted from each trial with a custom-written MATLAB script and maximal joint torque (in Nm) will be calculated by multiplying peak force with the lever arm and taking the average of the 3 trials. Knee and plantar flexion maximal voluntary isometric contractions are corrected for gravity by subtracting the gravitational torque in rest from the outcomes. Maximal joint torque will be normalized by dividing it by body weight (Nm/kg).

3. Three-dimensional freehand ultrasonography

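### For outcomes analysed on both legs, the default mixed model, read as a longitudinal structure, sets the covariance between the two legs' changes to zero, although the sample size assumes a correlation of 0.1

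*Combined protocol and SAP*

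**What the plan says.** The Statistics section tests the intervention through the time-by-group interaction in a linear mixed model. On dependence it says that "The random effects in these models can correct for the correlation between repeated observations within the same subject". The covariance structure is for "longitudinal dependencies within the participant will be applied with a random intercept for participant (legs are nested within participants". The matrix is specified as "with a compound symmetry covariance matrix, unless an unstructured covariance matrix results in a better fit", where a better fit means an AIC drop of more than 2. No participant-by-time term is listed. The section does not say whether the matrix belongs to the leg or the child, or whether it is 2x2 or 4x4.

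The Sample size section sizes the same quantity, requiring 39 "independent observations per group to compare the evolution over time between the intervention and control groups". It then allows for two legs per child with an intraclass correlation of 0.1, "based on literature of general health parameters": "the estimated design effect was 1.1, resulting in 43 clustered legs, or 22 bilaterally affected participants per group". For a mixed sample it adds: "A group including both uni- and bilaterally affected children would require a sample size between 39 and 43".

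The Participant characteristics section says: "These clinical examination parameters will be used to define the most affected leg for bilaterally affected children". The Statistics section does not mention this leg again, so the plan does not state which outcomes use one leg and which use both.

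**The concern.** Two legs of one child share the training, the effort and the test day, so their changes may be correlated. The sample size allows for this. The analysis should allow for it as well, because the standard error of the interaction depends on the covariance between the two legs' changes. The plan relies on the random effects for within-child correlation, but the only random effect it names is an intercept, which cancels when PRE is subtracted from POST.

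At stake is the true size of the 1% test for outcomes that could be analysed on both legs: joint torque, muscle volume, muscle length, echo-intensity, unilateral heel raise and lateral step-up. Two analysts following the text could also fit models with different standard errors to the same data.

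**Working it through.** **Inputs from the plan.** Sample size section: d = 0.8, type I error 0.01, power 80%, ρ = 0.1, cluster size 2. Study design section: two time points and 1:1 allocation. Statistics section: the model described above.

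**Assumptions.** ρ of 0.3, 0.5 and 0.8; equal variance for every leg; the between-leg variances in step 4; and, for a mixed sample, 14 bilateral plus 14 unilateral children per group (14×2 + 14 = 42 legs, inside the plan's 39 to 43). Age and GMFCS covariates are left out.

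**Step 1: the plan's own figure.** A two-sided noncentral t calculation gives power 0.798 with 38 per group and 0.810 with 39, so 39 reproduces. Then 39 × [1 + 0.1 × (2 − 1)] = 42.9, or 43 legs, and 43/2 = 21.5, or 22 children.

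**Step 2: covariance between the two legs' changes.** For legs A and B:

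Cov(change A, change B) = Cov(A post, B post) − Cov(A post, B pre) − Cov(A pre, B post) + Cov(A pre, B pre).

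Let τ² be the participant-intercept variance.
- Compound symmetry over time, per leg: all four terms are τ², so the sum is 0.
- Unstructured 2x2, per leg: the cross-leg terms are still all τ², so the sum is 0.
- Compound symmetry over the child's four values, with common covariance c: all four terms are τ² + c, so the sum is 0.
- Compound symmetry across legs within a visit, with extra same-visit covariance k: the terms are τ² + k, τ², τ² and τ² + k, so the sum is 2k.
- Unstructured 4x4 over the child: the sum is free.

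In the third case τ² and c enter only as a sum, so the intercept and the matrix cannot be separately estimated. Among the longitudinal readings, only the per-leg one makes both stated components identifiable.

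As a check, one simulated data set with correlated leg changes was fitted with the per-leg model. The interaction standard error was 0.2675, the same as from a t-test treating legs as independent. A child-mean analysis gave 0.3338.

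**Step 3: size under the per-leg reading.** The true variance exceeds the modelled variance by DE = 1 + ρ if all children are bilateral. With 14 + 14, DE = [28(1 + ρ) + 14]/42 = 1 + 2ρ/3. The size is 2 × [1 − Φ(2.576/√DE)]. At ρ = 0.1 with all bilateral, the modelled standard error is 1/√1.1 = 95% of the true one.

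| ρ | Modelled SE / true SE, all bilateral | Size, all bilateral | Size, 14 + 14 |
|---|---|---|---|
| 0.1 (plan) | 95% | 1.4% | 1.3% |
| 0.3 (assumed) | 88% | 2.4% | 1.9% |
| 0.5 (assumed) | 82% | 3.5% | 2.6% |
| 0.8 (assumed) | 75% | 5.5% | 3.8% |

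The 2x2 fallback does not change this.

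**Step 4: the child as subject.** Set a leg's time-varying variance to 1 = P + E (participant-by-time plus residual), so ρ = P, and let L be the between-leg variance. Compound symmetry over four values pools the leg, time and leg-by-time contrasts, so true variance / modelled variance = (E + 2P) / [E + 2(P + L)/3]. At ρ = 0.1:
- L = 0: 1.1/0.967 = 1.138, size 1.6%.
- L = 0.5: 1.1/1.3 = 0.846, size 0.5%.
- L = 1: 1.1/1.633 = 0.673, size 0.2%.

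The next table adds the AIC switch to a 4x4 matrix. It comes from simulation with 22 bilateral children per group and 15,000 null trials per setting (Monte Carlo error about 0.1 point).

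| L (assumed) | ρ = 0.1 | 0.3 | 0.5 | 0.8 |
|---|---|---|---|---|
| 0 | 1.7% | 2.9% | 2.2% | 1.6% |
| 0.5 | 0.9% | 1.4% | 1.8% | 1.5% |
| 1 | 1.3% | 1.4% | 1.5% | 1.5% |

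An uncorrected 4x4 matrix by itself gives 1.4 to 1.5% at every ρ, which is a small-sample bias unrelated to ρ.

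**Step 5: a model with a participant-by-time effect.** In simulation (100,000 null trials per setting) its size at the four ρ values was 0.92, 0.99, 1.02 and 1.01% with all children bilateral, and 0.95, 1.03, 0.98 and 1.02% with 14 + 14. An unweighted child-mean t-test in the 14 + 14 sample gave 1.02, 0.99, 0.94 and 1.01%.

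**Step 6: power with the correct variance.** With 22 bilateral children per group, the noncentrality is 0.8/√[(1 + ρ)/22] on 42 degrees of freedom. Power is 80.5% at ρ = 0.1, 72.1% at 0.3 and 64.3% at 0.5. With 14 + 14, the noncentrality is 0.8 × √[14/(1 + ρ) + 7] on 54 degrees of freedom, and power is 80.7%, 75.6% and 71.1%.

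**The case against.** The strongest objection is that the defect is conditional. No passage states that a given outcome is analysed on both legs. The sample size speaks only of possible clustering, and a most affected leg is defined. If that leg is the unit of analysis, nothing here applies. This stands as a limit on scope. It does not remove the point, because the Statistics section itself describes legs nested in participants and the sample size counts legs.

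A second objection is that dependence is described within the participant, so the child is the subject and AIC can select a 4x4 matrix that carries the correlation. This stands in part. A reader might infer that the type I error always inflates and keeps growing as the legs change more alike. The documents do not support that. With the child as subject, the default can be conservative, and after the AIC switch the size lies between about 0.9% and 2.9% with no steady rise. The 3.5% and 5.5% figures belong only to the per-leg reading, at correlations that the plan does not give. Nor does the AIC rule clearly rescue the plan, since the matrix dimension is not stated and a 2x2 fallback leaves the covariance at zero.

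Third, compound symmetry across legs within a visit would give the right size. That is correct, but it is not a structure for dependence over time, which is what the text describes.

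Fourth, a reader might see a contradiction between the two sections. A design effect used for sizing need not reappear as a model parameter, and the planned numbers still give about 80% power at ρ = 0.1. The problem is in the analysis model, not in the sample size arithmetic.

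**Conclusion.** The concern holds for outcomes analysed on both legs, and it is minor. The algebra in step 2 is exact and needs no parameter values: under either longitudinal reading of compound symmetry, the default model gives zero covariance between the two legs' changes.

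At the only documented correlation, 0.1, the consequence is small on the per-leg reading: about 1.4% instead of 1% with all children bilateral, or 1.3% in the 14 + 14 mix. Larger errors need both that reading and a correlation above 0.1. The plan's 0.1 does not come from two legs of one child, so a higher value cannot be ruled out, but the documents give no evidence for one. With the child as subject, the direction depends on the between-leg variance, which is also undocumented.

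Bilateral heel raise, sit-to-stand, standing long jump, gross motor function and the 1-minute walk give one value per child and are unaffected. So is any analysis restricted to the most affected leg.

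**What to change.** In the Statistics section, list which outcomes use both legs and which use only the most affected leg. For the two-leg outcomes, replace the participant intercept and the compound-symmetry/AIC rule with random effects for participant, leg within participant and participant-by-time, with Satterthwaite or Kenward-Roger degrees of freedom. Other structures that let the two legs' changes correlate would also close the gap, provided the subject and dimension are named. An analysis of each child's mean change is an acceptable equivalent or sensitivity check. For one-value-per-child outcomes, keep the PRE/POST covariance alone.

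The cost is a change of SAP wording and one or two lines of SPSS syntax, with no new data. Compared with the per-leg model and all children bilateral, confidence intervals widen by about 5% at ρ = 0.1 (√1.1 = 1.049), and by 14% and 22% at assumed values of 0.3 and 0.5. Power stays at about 80% at ρ = 0.1. If the true correlation is higher, power falls below the stated 80%: to about 72% at 0.3 and 64% at 0.5 with 22 bilateral children per group, or 76% and 71% with the 14 + 14 mix.

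### As the model is listed, the adjustment for age and GMFCS level barely reaches the time×group test of treatment: no factor-by-time terms are given

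*Combined protocol and SAP*

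**What the plan says.** All of the model text is in the Statistics section of the combined protocol and SAP.

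- **Effect tested.** Linear mixed models are to "evaluate the difference in evolution over time between the control and intervention group (time*group interaction effect"), and also to estimate the change "between PRE and POST within each group (time effect").
- **Reason for the covariates, given twice.** "The models will be adjusted for age and GMFCS level as covariates as these were used to allocate the children", and again "Adjustment for age (categorical variable: <8 years and >8 years) and GMFCS level will be included as these were used to allocate the children".
- **Mean model.** "A full-factorial time*group mean model adjusted for age and GMFCS level, with a compound symmetry covariance matrix". The factorial structure is attached to time and group. No product of age or GMFCS level with time is listed, and no adjusted change-score model is given.
- **Covariance.** Compound symmetry, "unless an unstructured covariance matrix results in a better fit" (AIC lower by more than 2), with a random intercept for participant and legs nested within participant.

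The Study design section gives two assessments (PRE and POST) and minimisation on age (2 levels) and GMFCS (3 levels), 1:1, with probability 0.75. The Sample size section takes d = 0.8, α = 0.01 and 80% power on an independent-samples t-test, which "required 39 independent observations per group to compare the evolution over time between the intervention and control groups". A design effect of 1.1 follows, "resulting in 43 clustered legs, or 22 bilaterally affected participants per group".

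**The concern.** Treatment is judged on a difference in change. An age or GMFCS main effect describes a difference in level that is the same at PRE and at POST. Such a term has no route into the difference in change unless it is also allowed to vary with time. The plan gives allocation as the reason for adjusting, so a reader will take the treatment estimate to be adjusted for the minimisation factors, and the listed model does not deliver that.

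What is at stake is precision and the actual error rate. Minimisation balances the two factors between groups. If they predict 12-week change, that balance makes the difference in mean change less variable than the unadjusted standard error assumes. Intervals are then wider than they need to be, and the test can fall below its nominal 1%.

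**Working it through.** **1. The plan's own figures reproduce.** With d = 0.8 and two-sided α = 0.01, exact t-test power is 0.7975 at 38 per group and 0.8104 at 39. The design effect is 1 + 0.1 × (2 − 1) = 1.1, so 39 × 1.1 = 42.9, rounded to 43 legs, and 43 / 2 = 21.5, rounded to 22 children. This calculation is for an unadjusted comparison of change.

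**2. Why main effects cancel.** For a child with fixed covariates x, the main-effects model is E(Y_t) = b0 + b1·t + b2·g + b3·t·g + x′c, with t = 0 at PRE and 1 at POST. Split each pair into:

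- the change D = POST − PRE, with E(D) = b1 + b3·g, which contains no x;
- the weighted combination of PRE and POST that is uncorrelated with D. Here x′c appears, but b0 and b2 leave the intercept and group term free, so this part says nothing about b1 or b3.

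The estimate of b3 is therefore the raw difference in mean change with its pooled standard error, whatever c is. The argument does not need equal variances, so it covers compound symmetry and an unstructured time covariance.

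**3. Numerical check.** REML fits to simulated complete data (44 children; all data values assumed; age deliberately imbalanced) gave the same results under both covariance structures. Entries are the time×group estimate (SE).

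| Data | No covariates | Main effects | Factor×time added |
|---|---|---|---|
| One leg per child | 0.402462 (0.257505) | 0.402462 (0.257505) | 0.431086 (0.274848) |
| Unilateral/bilateral mix, random intercept for child | 0.312285 (0.199609) | 0.312285 (0.199609) | 0.667796 (0.209481) |

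Only the factor×time terms change the test. The size of the movement is not representative, because these data were not minimised.

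**4. Where cancellation is not exact.**

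- Missing POST values: with 8 of 78 missing at random given PRE (R² = 10%, PRE–POST correlation 0.7 assumed), main effects shift the estimate by 0.049 SE on average, with an SE ratio of 0.999. Factor×time terms give an SE ratio of 0.950.
- A participant-level unstructured matrix over legs and times, in a unilateral/bilateral mix: the estimate moves from 0.3012 to 0.3071 and the SE from 0.19845 to 0.19842, with complete data.
- Only if PRE and POST on the same child were uncorrelated would main effects alter the SE materially, and that is not plausible.

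**5. Size with 78 single observations (2 × 39).** Assumptions: R² as shown; GMFCS I/II/III 45/35/20%; age 50/50; the two factors sharing R² equally; the plan's minimisation. There were 40,000 null and 20,000 alternative trials per setting (Monte Carlo SE about 0.0005 and 0.003).

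| R² | Type I, planned | Type I, with terms | Power, planned | Power, with terms | 99% interval width ratio |
|---|---|---|---|---|---|
| 0 | 0.0095 | 0.0097 | 0.814 | 0.809 | 1.004 |
| 5% | 0.0078 | 0.0096 | 0.816 | 0.831 | 0.979 |
| 10% | 0.0069 | 0.0097 | 0.822 | 0.856 | 0.952 |
| 20% | 0.0046 | 0.0092 | 0.830 | 0.896 | 0.898 |

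The mechanism is visible in the ratio of true to model-based SE for the planned test, which under good balance is about √(1 − R²): 0.975, 0.949 and 0.894 for 5, 10 and 20%, against simulated 0.978, 0.951 and 0.909. Under minimisation the terms move the estimate by only 0.06/0.08/0.10/0.14 SE on average.

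If the factors act only in the trained arm, planned type I error is 0.0088/0.0092/0.0070 at 5/10/20%, and power is 0.811/0.814/0.817 as planned against 0.817/0.829/0.850 with the terms.

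**6. Size with 22 bilateral children per group, two legs each.** With ρ = 0.1 applied to change, only 10% of leg-level variance lies between children. Age and GMFCS level are child-level, so they cannot explain more than 10%. Under the same factor mix (4,000 alternative and 6,000 null trials; Monte Carlo SE of power about 0.006):

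| R² | Power, planned | Power, with terms | Type I, planned |
|---|---|---|---|
| 0 | 0.794 | 0.788 | 0.0105 |
| 2.5% | 0.814 | 0.821 | 0.0102 |
| 5% | 0.805 | 0.830 | 0.0088 |
| 10% (cap) | 0.815 | 0.878 | 0.0045 |

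Allowing for Monte Carlo error and repeat runs, the change in power is about −1.5 to +2.6 points for R² from 0 to 5%, and about +6 points at the cap.

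**The case against.** The strongest reply is that nothing the plan promises is broken. The covariate terms are not written out, so main effects only is a reading and not a statement. The trial was sized on an unadjusted t-test, and planned power stays at 0.81 to 0.83 with 78 observations. Minimisation keeps the groups alike, so the estimate hardly moves. R² appears nowhere in the documents, and normalising torque to body weight and muscle size to fibula length may lower it. At R² = 0 the extra terms cost a little power. On this view only the wording needs clarifying.

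Much of that stands. The factor×time terms are absent from the list, not excluded by it. The gain is conditional on R², and for two-leg outcomes it is small below the 10% cap. In a single trial the terms can even raise the standard error, as in the two illustrative datasets. Main effects also have a use: they inform comparisons of level and enter slightly when POST values are missing.

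What does not stand is that wording is the whole issue. The plan twice justifies the adjustment by the allocation factors, and on the natural reading the treatment test is essentially the same with or without them. That mismatch holds whatever R² is.

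**Conclusion.** The concern holds with limits. On the main-effects reading, the time×group test is in effect unadjusted for the minimisation factors. The cost is lost precision, plus a conservative test when the factors explain a material share of change: type I error of about 0.007 at R² = 10% and 0.005 at 20% with 78 single observations, and less departure if the factors act only in the trained arm. The sizes rest on an assumed R² and an assumed factor mix.

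Four stronger readings might be inferred, and the documents support none of them:

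- *The treatment estimate is biased or false positives are inflated.* Allocation is balanced on both factors, and the departures in type I error are downwards.
- *The trial falls short of its stated power because of this.* The sample size rests on the unadjusted comparison, which keeps about 80%.
- *The test is conservative in general.* At low R², or with effects in the trained arm only, the departure is slight. The 20% row is not available to two-leg outcomes under the plan's ρ = 0.1, although that cap does not bind child-level outcomes such as the walk test.
- *Cancellation is exact under any covariance the plan could mean.* It is exact for complete pairs with a time covariance as described, and only approximate in the cases in step 4 of the working.

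The change is worth making before analysis, but the trial's validity does not depend on it.

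**What to change.** - Write out the covariate terms. For the time×group test, add age×time and GMFCS×time to the mean model alongside the main effects.
- Fix the age category at its value at allocation. Age is recorded at each assessment, and a category updated at POST would be a different covariate.
- Keep the within-group PRE–POST effects, but report them as estimated marginal contrasts with stated weights over the age and GMFCS levels. Once the terms are in, the raw time coefficient refers to the reference levels only.
- If main effects only are intended, say so, and do not describe the treatment estimate as adjusted for the minimisation factors.

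Cost: a few lines of SAP text and three degrees of freedom (one for age, two for GMFCS level), with no new data. If the factors do not predict change, the loss is about half a point of power at 78 observations (0.814 to 0.809) and about 1 point with 44 children (0.492 to 0.479 with one observation each; 0.6 to 1.5 points with two legs each).
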